9.7 APPENDIX G: PAIN ANXIETY SYMPTOMS SCALE-20 (PASS-20)

Name: _____

Date: _____

PAIN ANXIETY SYMPTOMS SCALE-20 (PASS-20)

Individuals who experience pain develop different ways to respond to that pain. We would like to know what you do and what you think about when in pain. Please use the rating scale below to indicate how often you engage in each of the following thoughts or activities. Circle any number from 0 (NEVER) to 5 (ALWAYS) for each item.

| | | NEVER | | ALWAYS | | |
|-----|---|--------------|---|---------------|---|---|
| 1. | I think that if my pain gets too severe, it will never decrease | 0 | 1 | 2 | 3 | 4 |
| 2. | When I feel pain I am afraid that something terrible will happen | 0 | 1 | 2 | 3 | 4 |
| 3. | I go immediately to bed when I feel severe pain | 0 | 1 | 2 | 3 | 4 |
| 4. | I begin trembling when engaged in activity that increases pain | 0 | 1 | 2 | 3 | 4 |
| 5. | I can't think straight when I am in pain | 0 | 1 | 2 | 3 | 4 |
| 6. | I will stop any activity as soon as I sense pain coming on | 0 | 1 | 2 | 3 | 4 |
| 7. | Pain seems to cause my heart to pound or race | 0 | 1 | 2 | 3 | 4 |
| 8. | As soon as pain comes on I take medication to reduce it | 0 | 1 | 2 | 3 | 4 |
| 9. | When I feel pain I think that I may be seriously ill | 0 | 1 | 2 | 3 | 4 |
| 10. | During painful episodes it is difficult for me to think of anything else besides the pain | 0 | 1 | 2 | 3 | 4 |
| 11. | I avoid important activities when I hurt | 0 | 1 | 2 | 3 | 4 |
| 12. | When I sense pain I feel dizzy or faint | 0 | 1 | 2 | 3 | 4 |
| 13. | Pain sensations are terrifying | 0 | 1 | 2 | 3 | 4 |
| 14. | When I hurt I think about the pain constantly | 0 | 1 | 2 | 3 | 4 |
| 15. | Pain makes me nauseous (feel sick) | 0 | 1 | 2 | 3 | 4 |
| 16. | When pain comes on strong I think I might become paralyzed or more disabled | 0 | 1 | 2 | 3 | 4 |
| 17. | I find it hard to concentrate when I hurt | 0 | 1 | 2 | 3 | 4 |
| 18. | I find it difficult to calm my body down after periods of pain | 0 | 1 | 2 | 3 | 4 |
| 19. | I worry when I am in pain | 0 | 1 | 2 | 3 | 4 |
| 20. | I try to avoid activities that cause pain | 0 | 1 | 2 | 3 | 4 |

Abbreviated Title: ACT Therapy for NF1Related Pain

Version Date: 02/19/2019

9.9 APPENDIX H: CENTER FOR EPIDEMIOLOGICAL STUDIES-DEPRESSION SCALE (CES-D)

Name: _____

Date: _____

CES-D

Please indicate how often you have felt this way during the last week.

3 = Most or all of the time (5 to 7 days a week).

2 = Occasionally or a moderate amount of time (3 to 4 days a week).

1 = Some or a little of the time (1 to 2 days a week).

0 = Rarely or none of the time (less than once a week).

| | | | | |
|---|---|---|---|---|
| 1. I was bothered by things that usually don't bother me. | 0 | 1 | 2 | 3 |
| 2. I did not feel like eating: my appetite was poor. | 0 | 1 | 2 | 3 |
| 3. I felt that I could not shake off the blues. | 0 | 1 | 2 | 3 |
| 4. I felt that I was just as good as other people. | 0 | 1 | 2 | 3 |
| 5. I had trouble keeping my mind on what I was doing. | 0 | 1 | 2 | 3 |
| 6. I felt depressed. | 0 | 1 | 2 | 3 |
| 7. I felt that everything I did was an effort. | 0 | 1 | 2 | 3 |
| 8. I felt hopeful about the future. | 0 | 1 | 2 | 3 |
| 9. I thought my life had been a failure. | 0 | 1 | 2 | 3 |
| 10. I felt fearful. | 0 | 1 | 2 | 3 |
| 11. My sleep was restless. | 0 | 1 | 2 | 3 |
| 12. I was happy. | 0 | 1 | 2 | 3 |
| 13. I talked less than usual. | 0 | 1 | 2 | 3 |
| 14. I felt lonely. | 0 | 1 | 2 | 3 |
| 15. People were unfriendly. | 0 | 1 | 2 | 3 |
| 16. I enjoyed life. | 0 | 1 | 2 | 3 |
| 17. I had crying spells. | 0 | 1 | 2 | 3 |
| 18. I felt sad. | 0 | 1 | 2 | 3 |
| 19. I felt that people disliked me. | 0 | 1 | 2 | 3 |
| 20. I could not get going. | 0 | 1 | 2 | 3 |

9.10 APPENDIX I: NUMERIC RATING SCALE-11 (NRS-11)

[figure not shown]
I am going to ask you two questions about how much your plexiform neurofibroma tumor hurts.

First, where is the location of your most important tumor pain?

[figure not shown]
(Specify the location of that tumor: _____).

Below are lines with numbers from 0 to 10 where 0 means no pain and 10 means the worst pain you can imagine.

1. Please circle the one number that best describes that most important tumor pain at its worst during the past week.

2. Please circle the one number that best describes your overall tumor pain at its worst during the past week.

9.11 APPENDIX J: CHRONIC PAIN ACCEPTANCE QUESTIONNAIRE (CPAQ)

P - CPAC

CPAQ

Directions: Below you will find a list of statements. Please rate the truth of each statement as it applies to you. Use the following rating scale to make your choices. For instance, if you believe a statement is 'Always True,' you would write a 6 in the blank next to that statement.

| 0 | 1 | 2 | 3 | 4 | 5 | 6 |
|------------|------------------|-------------|----------------|------------|--------------------|-------------|
| Never True | Very rarely true | Seldom true | Sometimes true | Often true | Almost always true | Always true |

1. I am getting on with the business of living no matter what my level of pain is.
2. My life is going well, even though I have chronic pain.
3. It's OK to experience pain.
4. I would gladly sacrifice important things in my life to control this pain better.
5. It's not necessary for me to control my pain in order to handle my life well.
6. Although things have changed, I am living a normal life despite my chronic pain.
7. I need to concentrate on getting rid of my pain.
8. There are many activities I do when I feel pain.
9. I lead a full life even though I have chronic pain.
10. Controlling pain is less important than any other goals in my life.
11. My thoughts and feelings about pain must change before I can take important steps in my life.
12. Despite the pain, I am now sticking to a certain course in my life.
13. Keeping my pain level under control takes first priority whenever I'm doing something.
14. Before I can make any serious plans, I have to get some control over my pain.
15. When my pain increases, I can still take care of my responsibilities.
16. I will have better control over my life if I can control my negative thoughts about pain.
17. I avoid putting myself in situations where my pain might increase.
18. My worries and fears about what pain will do to me are true.
19. It's a relief to realize that I don't have to change my pain to get on with my life.
20. I have to struggle to do things when I have pain.

Scoring: Chronic pain acceptance questionnaire

Activities engagement: Sum items 1, 2, 3, 5, 6, 8, 9, 10, 12, 15, 19

Pain willingness: Reverse score items 4, 7, 11, 13, 14, 16, 18, 18, 20 and sum

Total: activity engagement + pain willingness

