3.3.1.6 Coping with Pain

The Chronic Pain Acceptance Questionnaire (CPAQ; (L. M. McCracken et al., 2004) was designed to assess one's ability to accept his or her pain, and is typically used with patients ages 18 years and older. Respondents answer 20 questions on a 0 (never true) to 6 (always true) rating scale, with higher scores indicating higher levels of acceptance. Scores are obtained on two subscales (Activities Engagement and Pain Willingness) and an Acceptance Total scale. Reliability and validity, and sensitivity to change have been demonstrated (Huggins et al., 2012; Vowles & McCracken, 2008). The CPAQ takes approximately 5 minutes to complete (See [Appendix J](#)).

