6 STATISTICAL SECTION

6.1 PRIMARY AND SECONDARY OUTCOMES

The primary objective of the trial is to compare pain interference mean score changes from baseline to 8 weeks between the ACT intervention group and the WL group. In the pilot study conducted by our group, mean scores on PII self-report went from 2.1 (1.0) to 1.5 (1.1), with paired differences having a mean change of -0.68 and SD=1.3. Based on this preliminary estimated change for the ACT group, and an assumption of no change in the WL group and a corresponding, reduced SD = 0.8, forty-one patients will be needed per group to have 80% power to detect a difference in change score between the two arms of -0.68, using a t-test with significance level of .05 (two-sided). Secondary analyses will be performed to compare between-group changes from baseline to 8 weeks and from baseline to 32 weeks on the following endpoints: disease-related quality of life, pain severity, pain-related anxiety, and depression. Given the wide age range of the study, we will stratify analyses by age (16 – 24 years; 25 – 59 years). Descriptive statistics will be computed on the primary and secondary outcome measures (means, standard deviations, etc.). If there are significant differences between the groups at baseline (for example, with respect to gender or number of patients on pain medication), analysis of covariance (ANCOVA) may be used to control for these differences statistically during follow-up analyses (treating baseline as a covariate). We also will assess for differences between the group randomized to ACT and the WL group on primary and secondary outcomes, particularly comparing primary results from 0 to 8 weeks for ACT vs. 8 to 16 weeks for WL (receiving ACT starting at 8 weeks); if the results are similar (for example, $p>0.30$ approximately), we will combine these groups to report the overall effect of ACT for 8 weeks, and also examine changes from baseline to 8 weeks and 8 to 16 weeks using an appropriate statistical test. Finally, based on a priori hypotheses and prior literature, we will test for indirect effects of acceptance and psychological flexibility with simple mediation model analyses. We will generate 5,000 bootstrapped samples using Preacher and Hayes' (Preacher & Hayes, 2004) INDIRECT macro. Post-treatment scores will be used for these analyses. Additionally, we will examine whether a previous cognitive diagnosis (ADHD or learning disability), reading ability, disease characteristics (stable vs. progressive disease, location of plexiform neurofibroma), or recent life events, relate to changes over time in the primary outcome with an ANOVA, and if so

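### The printed CPAQ scoring key counts item 18 twice and leaves item 17 out of both subscales; if it is used as printed, Pain Willingness and the Acceptance Total are mis-scored, with a probably small effect on a secondary mediation analysis.

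*Combined protocol and SAP*

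**What the plan says.** Section 3.3.1.6 describes the CPAQ: "Respondents answer 20 questions on a 0 (never true) to 6 (always true) rating scale". It continues: "Scores are obtained on two subscales (Activities Engagement and Pain Willingness) and an Acceptance Total scale". It gives no item numbers.

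Appendix J (section 9.11) prints the 20 statements and then a key of three lines:

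- The first line assigns 11 items to Activities Engagement; item 17 is not among them.
- The second line reads "Pain willingness: Reverse score items 4, 7, 11, 13, 14, 16, 18, 18, 20 and sum".
- The third line defines the overall score as the two subscales added together.

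Item 17 is on the form: "17. I avoid putting myself in situations where my pain might increase". Item 18 is a different statement, about worries and fears over what pain will do.

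Pain acceptance is named as a potential mediator in objective 1.1.2.4. Section 6.1 says "we will test for indirect effects of acceptance and psychological flexibility with simple mediation model analyses", using post-treatment scores and 5,000 bootstrap samples. It does not say whether acceptance means the Total or a subscale.

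**The concern.** The key does not cover the questionnaire. One administered item contributes to no score, and another counts double. Because the Total is the sum of the two subscales, it inherits the slip; Activities Engagement does not.

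The protocol supports its choice of the CPAQ by citing reliability, validity and sensitivity to change. A score that omits an activity-avoidance item and double-weights a worry item is not quite the score those properties belong to. Avoidance is also something the intervention addresses directly: the fidelity checklist in Appendix T has an entry on avoidance versus acceptance.

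The slip would also be hard to notice. The willingness line still has nine entries and the score ranges look right. No other section gives a key against which it could be caught.

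**Working it through.** **Count.** The plan's own figure is 20 questions (section 3.3.1.6).

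- Activities Engagement: 1, 2, 3, 5, 6, 8, 9, 10, 12, 15, 19, which is 11 items.
- Items left over: 4, 7, 11, 13, 14, 16, 17, 18, 20, which is 9 items; 11 + 9 = 20.
- Pain Willingness as printed: 4, 7, 11, 13, 14, 16, 18, 18, 20, which is 9 entries but 8 distinct items.
- Printed key overall: 11 + 9 = 20 entries but 11 + 8 = 19 distinct items. Missing: 17. Duplicated: 18.

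The correction follows by elimination. Nine entries are printed, nine items remain, and only item 17 is unassigned. It is worded against acceptance, as a reverse-scored item should be.

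**Shift per patient.** Write x17 and x18 for the raw answers (0–6). The other willingness items cancel, so

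printed − corrected = 2(6 − x18) − [(6 − x17) + (6 − x18)] = x17 − x18.

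This lies between −6 and +6 and is zero only when the two answers agree. For example, x17 = 5 and x18 = 2 contribute 4 + 4 = 8 under the printed key and 1 + 4 = 5 under the corrected key, a shift of +3.

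**Ranges.** Under both keys Pain Willingness runs from 0 to 9 × 6 = 54, Activities Engagement from 0 to 11 × 6 = 66, and the Total from 0 to 120.

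**Closeness to the corrected score.** The documents give no item-level data, so this part rests on assumptions. Suppose all items, scored towards acceptance, have equal variance and a common correlation ρ. The sum of nine items then has variance proportional to 9 + 72ρ. The shift has variance 2(1 − ρ) and, by symmetry, no covariance with the corrected sum. Hence

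- Pain Willingness: r = √[(9 + 72ρ)/(11 + 70ρ)]. At ρ = 0.3, √(30.6/32) = 0.978; at ρ = 0.5, √(45/46) = 0.989.
- Total (20 items): r = √[(20 + 380ρ)/(22 + 378ρ)]. At ρ = 0.3, √(134/135.4) = 0.995; at ρ = 0.5, √(210/211) = 0.998.

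A simulation on the actual 0–6 scale agrees. It used one common factor, items centred at 3, item SD before rounding of 1.0 to 2.0, answers rounded and clipped, and 200,000 response sets per setting:

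| Assumed ρ | Items 17 and 18 differ | Mean absolute shift | r, Pain Willingness | r, Total |
|---|---|---|---|---|
| 0 | 73–85% | 1.13–2.04 | 0.9041–0.9047 | 0.9535–0.9538 |
| 0.3 | 68–81% | 0.94–1.69 | 0.9760–0.9767 | 0.9943–0.9945 |
| 0.5 | 63–76% | 0.79–1.41 | 0.9876–0.9882 | 0.9973–0.9974 |
| 0.7 | 55–70% | 0.62–1.09 | 0.9937–0.9943 | 0.9987–0.9988 |
| 0.9 | 35–53% | 0.36–0.62 | 0.9976–0.9982 | 0.9995–0.9996 |

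The mean shift is about zero in every setting, because the two items were given the same mean.

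**The case against.** The strongest reply is that this is a one-digit slip in an appendix. The CPAQ is a published instrument cited in section 3.3.1.6, and the intended item is obvious by elimination. Questionnaires are completed on computer or tablet (section 4.1) and analysed in SAS (section 6.1), but nothing says which key was programmed. The repeated 18 could even be a text-reading error, since digits on other instrument pages also look unreliable. If the Total is the mediator, the printed and corrected scores are almost interchangeable. Activity avoidance is also measured by the eight-item Avoidance subscale of the PIPS (section 3.3.1.7), which serves the same mediation analysis.

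Much of this stands, and it limits the size of the point. It does not remove the point: Appendix J is the only scoring rule the protocol states, and following it gives the wrong score.

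Three stronger readings are tempting, and the documents do not support them.

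- A reader might infer that acceptance scores are wrong for most patients. That requires the printed key to have been programmed, and most patients to answer items 17 and 18 differently. The documents show neither, and at an assumed correlation of 0.9 the share affected is 35–53%.
- A reader might imagine worse outcomes, such as item 18 being reversed twice or the duplicate being dropped to leave eight items. Nothing suggests that either was done.
- A reader might assume that re-scoring is always possible. Section 4.1 describes data entry and secure storage but does not say that item-level responses are kept.

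**Conclusion.** The key is wrong as written, and the point is minor. Three parts rest on counting and algebra alone: item 17 is unscored, item 18 is counted twice, and literal use shifts Pain Willingness and the Total by x17 − x18.

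That the consequence is small is a judgement. It assumes inter-item correlations of roughly 0.3 to 0.5, and no large difference between the arms in how items 17 and 18 move. The second assumption matters because high correlations alone do not rule out a between-arm shift. If ACT lowered item 17 by one point more than item 18 relative to wait-list, the printed key would understate the between-arm difference in acceptance by one point.

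Only the acceptance part of the mediation analysis is exposed. The primary endpoint (the Pain Interference Index), eligibility and the sample size do not use the CPAQ. The reason to act is that the error is definite and the correction cheap; there is no evidence of serious bias.

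**What to change.** In Appendix J, make the nine reverse-scored Pain Willingness items 4, 7, 11, 13, 14, 16, 17, 18 and 20. The two subscales then cover all 20 items once each, and the ranges do not change.

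Before the mediation analysis is run, confirm the line on the original PDF page and compare the programmed key with the corrected list item by item, since a range check will not do. Re-score any CPAQ already scored from the printed key where the item responses are available.

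The cost is one number in an appendix, a short check of the scoring program and, if needed, a re-run of the scoring. Where item responses were kept, no new data are required.

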9.12 APPENDIX K: PSYCHOLOGICAL INFLEXIBILITY IN PAIN SCALE (PIPS)

Below you will find a list of statements. Please rate how true each statement is for you right now by circling a number next to it.

| 1 | 2 | 3 | 4 | 5 | 6 | 7 |
|--|------------------|-------------|----------------|------------|--------------------|-------------|
| Never true | Very rarely true | Seldom true | Sometimes true | Often true | Almost always true | Always true |
| 1. I cancel planned activities when I am in pain. 1 2 3 4 5 6 7 | | | | | | |
| 2. I say things like “I don’t have energy”, “I am not well enough”, “I don’t have time”, “I don’t dare”, “I have too much pain”, “I feel too bad”, or “I don’t feel like it”. 1 2 3 4 5 6 7 | | | | | | |
| 3. I need to understand what is wrong in order to move on. 1 2 3 4 5 6 7 | | | | | | |
| 4. Because of my pain, I no longer plan for the future. 1 2 3 4 5 6 7 | | | | | | |
| 5. I avoid doing things when there is a risk it will hurt or make things worse. 1 2 | | | | | | |
| 3 4 5 6 7 | | | | | | |
| 6. It is important to understand what causes my pain. 1 2 3 4 5 6 7 | | | | | | |
| 7. I don’t do things that are important to me to avoid pain. 1 2 3 4 5 6 7 | | | | | | |
| 8. I postpone things because of my pain. 1 2 3 4 5 6 7 | | | | | | |
| 9. I would do anything to get rid of my pain. 1 2 3 4 5 6 7 | | | | | | |
| 10. It’s not me that controls my life, it’s my pain. 1 2 3 4 5 6 7 | | | | | | |
| 11. I avoid planning activities because of my pain 1 2 3 4 5 6 7 | | | | | | |
| 12. It is important that I learn to control my pain. 1 2 3 4 5 6 7 | | | | | | |

Abbreviated Title: ACT Therapy for NF1Related Pain

Version Date: 02/19/2019

9.13 APPENDIX L: LIFE EVENTS CHECKLIST

Name: _____ Date: _____

Please place a checkmark next to the events that **you** have experienced during the **past 6 months**.

| | |
|--|---|
|  1. Birth or adoption of a sibling by parent |  18a Hospitalization |
| |  18b Please specify # of days: ____ 1-5 ____ 6-10 ____ 11-15 ____ 16+ |
|  2. Marriage of a parent |  18c Reason hospitalized: _____ |
|  3. Divorce of parents |  19a Hospitalization of your parent |
|  4. Marital separation of parents |  19b Please specify # of days: ____ 1-5 ____ 6-10 ____ 11-15 ____ 16+ |
|  5. Death of a grandparent |  20. Discovery of a family member's serious illness |
|  6. Close family member leaving home for an extended period |  21. Discovery of a serious illness (please specify: _____) |
|  7. Loss of job by parent |  22. Disclosure of diagnosis to others |
|  8. Financial hardship (e.g., difficulty paying bills) |  23. One or more changes in residence |
|  9. Family gets financial assistance |  24. Family member experiencing problems with drugs or alcohol |
|  10. Death of a parent |  25. Substantial change in peer group |
|  11. Death of a sibling |  26. Teased in school/college |
|  12. Death of a peer |  27. Problems with school administration |
|  13. Move to a new school/college/job |  28. Teacher reporting behavior problems in school/college |
|  14. Repeated a grade or college course |  29. Other stressful event occurring in family Please specify _____. |
|  15. Suspension from school/college |  30. Experienced a change in primary caregiver(s). Please specify _____. |
|  16. Decline in school grades or work performance |  31. Parent has serious medical condition. Please specify _____. |
|  17. Significant number of school/work absences (16 or more) |  32. Giving birth or adopting a child |

Abbreviated Title: ACT Therapy for NF1 Related Pain

Version Date: 02/19/2019

____ 33. Getting married

____ 34. Separated from spouse or significant other

____ 35. Divorced

____ 36. Death of your spouse

____ 37. Death of your child

____ 38. Experiencing legal issues

____ 39. Experiencing stress related to a serious illness

____ 40. Discovery of a serious illness for your child

____ 41.a Hospitalization of your child

41.b Please specify # of days

____ 1-5 ____ 6-10 ____ 11-15 ____ 16+

____ 42. Loss of job

____ 43. Other stressful event related to work or school.

Please specify _____.

Check here if none of the above events have occurred in your life in the past 6 months.

Please take a few seconds to make sure you have reviewed every item on page 1 and page 2. Thank you for filling out this form!

Abbreviated Title: ACT Therapy for NF1 Related Pain

Version Date: 02/19/2019

9.14 APPENDIX M: PAIN MANAGEMENT INVENTORY

Pain Management Inventory

(1) In the past month, have you taken any medication for your pain? Yes No
If no, skip to question (2). If yes, please provide the following information:

Medication 1: Name _____ Dose _____

How often do/did you take this medication? (check one)

| | | | | |
|--------------------------|--------------------------|--------------------------|--------------------------|--------------------------|
|  |
| Less than once a month | 1-3 times a month | Once a week | 2-4 times a week | Daily |

Medication 2: Name _____ Dose _____

How often do/did you take this medication? (check one)

| | | | | |
|--------------------------|--------------------------|--------------------------|--------------------------|--------------------------|
|  |
| Less than once a month | 1-3 times a month | Once a week | 2-4 times a week | Daily |

(2) In the past month, have you done any behavioral techniques for the purpose of managing your pain besides ACT (for example, yoga, relaxation, exercise)? Yes No

If yes, please list and provide the following information:

1: Name _____

How often do you do this?

| | | | | |
|--------------------------|--------------------------|--------------------------|--------------------------|--------------------------|
|  |
| Less than once a month | 1-3 times a month | Once a week | 2-4 times a week | Daily |

2: Name _____

How often do you do this?

| | | | | |
|--------------------------|--------------------------|--------------------------|--------------------------|--------------------------|
|  |
| Less than once a month | 1-3 times a month | Once a week | 2-4 times a week | Daily |

(3) In the past month, have you done any other techniques for the purpose of managing your pain? Yes No

If yes, please list and provide the following information:

Name _____

How often do you do this?

| | | | | |
|--------------------------|--------------------------|--------------------------|--------------------------|--------------------------|
|  |
| Less than once a month | 1-3 times a month | Once a week | 2-4 times a week | Daily |

Abbreviated Title: ACT Therapy for NF1 Related Pain

Version Date: 02/19/2019

